The proposed project will evaluate the effectiveness of three different implementation strategies for integrating MI into the YNHH's internal medicine hospitalist service and other general medical inpatient units. Specifically, we will randomize 30 Healthcare providers to one of three conditions: (1) a continuing medical education workshop that "shows" the healthcare providers MI (the control condition, referred to as SEE ONE); (2) a 'see one, do one' apprenticeship model involving workshop training plus live supervision of bedside practice (DO ONE); and (3) ordering MI from CL after learning about it in a workshop (ORDER ONE). After receiving the respective MI training, each Healthcare provider will be followed for provision of MI to study-eligible/consented patients. In ORDER ONE, healthcare providers may elect to conduct MI themselves or order it to be conducted by Psychiatrists from the CL service.

After the Healthcare providers have attended their respective workshops, research staff will identify substance using patients in need of a MI intervention. Research staff will independently screen, assess and obtain consent from eligible patients who are admitted to the internal medicine hospitalist service and other general medical inpatient units. Patients will be potentially included if they are assigned to a participating Healthcare provider according to the hospital's usual clinical administrative procedures. Thus, patients will follow the randomization condition of their Healthcare provider, though Healthcare provider will not know which patients on their caseloads have enrolled in the study. This approach will permit a naturalistic test of the Healthcare provider's ability to identify and intervene using MI with patients who have substance use problems. Each Healthcare provider will be followed until he or she has

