Primary outcomes will be 1) the percentage of MI sessions, as verified by audio recordings, conducted among each Healthcare provider 40 consecutively enrolled study patients, 2) independently rated MI adherence and competence ratings of the sessions, and 3) the percentage of sessions conducted that meet a criterion level of adequate MI performance used in MI effectiveness¹⁸⁻²⁰ and clinician training trials.^{21,22} In addition, we will calculate the relative costs and cost effectiveness of the three conditions. Secondary outcomes will be 1) independently rated strength and frequency of patient statements that favor change in the sessions (called change talk) as a proxy for patient outcomes,^{23,24} and 2) themes related to implementation facilitators and barriers identified through qualitative interviews. The YNHH hospitalist and the psychiatric CL services will work closely with research staff to implement all aspects of this project.

Initially our main unit of randomization was the PAs within the YNHH hospitalist service. The director of the hospitalist service, [name], and [name], Chief PA of the hospitalist service, both co-investigators on this proposal, have committed the participation of the PAs on the service to the protocol. The service includes 33 PAs who work during days Mon-Fri on non-critical care general medical units. There is a turnover rate of about 2 per year that nets 40 PAs during the 4-year data collection phase of the project. Prior to randomization, [name], [name] and other members of the study team will meet with the PAs during staff meetings, wherein we will describe the project and elicit interest. Thereafter, we will screen PAs for eligibility and obtain written consent for their participation. PAs will next complete baseline assessment, including an audio recorded sample of their usual manner of interviewing an inpatient with a substance use problem. Following baseline assessments, a restricted randomization procedure will be used to allocate an equal number of PAs to the three conditions (10 PAs per condition).

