Originally this study focused on training PAs because they have become very prevalent and important midlevel providers in all practice settings in U.S. medicine. PAs have been used to address current health system and societal needs for primary care¹⁰⁵ and to reduce service costs¹⁰⁶ and house staff hours as mandated by the Accreditation Council of Graduate Medical Education.^{107,108} Moreover, they spend more time interacting with their patients than physicians within the YNHH hospitalist system, and recent work has shown PAs have the interest and capacity to learn behavioral intervention strategies such as MI.⁶⁹

While our initial goal was to randomize and enroll PAs only in this study, other healthcare providers have shown interest, ability to incorporate MI into their daily schedule and proven to be ideal candidates to include as a part of our cohort.

C. Study Setting

The study will take place on the general medical inpatient units of YNHH. The internal medicine hospitalist service (where we will be recruiting PA participants) consists of 8 teams, each comprised of an attending physician and 2-5 PAs. PAs typically see patients on more than one unit and see each assigned patient 1-2 times per day. Hospitalist patients are followed by one PA and one MD from the service. The hospitalist teams cover about 160 beds/day (range = 130-210) on 13 different units excluding intensive care units. In 2010, the service was responsible for approximately 9,900 discharges. The average length of stay for patients is 4 days. The psychiatric CL is available to all attending MDs and PAs for the assessment and initiation of treatment for mental health and addiction problems. Attendings and PAs order CL services via entry into the electronic medical record, which are viewed by a CL administrative assistant and CL staff throughout the day. Consultations are typically seen within 4-8 hours of placement, depending upon the acuity and time sensitivity of the requested consult. Non-urgent consults may be seen the next day if the caseload is high.

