- *Adequacy of sample size for primary hypotheses:* Effect sizes for power estimation for the continuous outcomes were based on studies by Miller et al.²³ (d=0.4 to 0.8) and [name] et al.²¹ (d=0.4 to 1.2). A review article by Apodaca and Longabaugh¹⁴⁸ also suggests that at least medium effect sizes are expected for the between-group comparisons. [name] et al.²¹ observed large effect sizes for the binary outcome comparison (meets criterion MI performance threshold, 53% vs. 18%); however, we conservatively assume a medium effect size for this comparison as well. Intra-class correlations accounting for expected within clinician variance were estimated based on Imel et al¹⁴⁹ and are expected to be small (in the 0.05 to 0.10 range). Feasibility constraints (i.e., 10 Healthcare providers per condition) limited the number of clusters (Healthcare providers) that we could consider. Finally, because we do not expect all Healthcare providers to identify substance using patients and use MI with them (i.e., our 1st hypothesis about MI uptake), we will require a larger sample size of study-enrolled patients to reach our targeted number of audio recorded MI sessions for hypothesis testing purposes. We estimate 80% of patients across conditions will receive MI. Based on these estimates and constraints, alpha level of 0.05 and power of 80%, 30 Healthcare providers and 40 patients per Healthcare provider will be sufficient for testing the primary hypotheses of the study. Table 2 shows the actual total sample size for the cluster-randomized design for continuous and binary outcomes, adjusted for a conservative estimate of MI uptake.

Table 2: Sample size estimates for the primary aims of the study based on alpha=0.05 for the pairwise comparisons of each condition to the control condition and 80% power.

Effect size	Total sample size for an ordinary RCT (3 arms)	ICC	Number of Healthcare provider	Average number of patients per Healthcare provider	Total sample size for a cluster RCT unadjusted for estimated MI uptake	Total sample size for a cluster RCT adjusted for estimated MI uptake
d=0.4	300	0.07	31	31	930	1116
40% vs 18%	195	0.1	30	17	510	765

3. Incremental cost-effectiveness analyses

The relative cost-effectiveness of the three MI implementation strategies will be assessed using both incremental cost-effectiveness ratios (ICERs) and cost-effectiveness acceptability curves (CEACs).

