SECTION VII: RECRUITMENT/CONSENT AND ASSENT PROCEDURES

1. **Targeted Enrollment: Give the number of subjects:**
a. targeted for enrollment at Yale for this protocol __see below__
b. If this is a multi-site study, give the total number of subjects targeted across all sites __n/a__

Participants will be Physician Assistants (PAs) who work at the Yale New Haven Hospital (YNHH) Internal Medicine Hospitalist service and 1200-1600 inpatients who are being cared for by a PA from the Hospitalist Service. All PAs on the Internal Medicine Hospitalist service are eligible to participate. We will obtain written informed consent from all the PAs who express interest in participation and MI training. The PAs will be randomized to one of three conditions that are outlined below. The inpatients who may be eligible subjects will be followed for inpatient care by one of the Internal Medicine hospitalist service PAs. While they will not be randomized, they will follow the randomization condition of their PA. Additionally, we have expanded our target for enrollment to other Healthcare providers (i.e. nursing staff, physician, etc.) who work at Yale New Haven Hospital (YNHH) within general medical inpatient units. Between the PAs and other healthcare providers we intend to enroll 30-40 participants.

2. **Indicate recruitment methods below.** Attach copies of any recruitment materials that will be used.

- | | | |
|--|---|-------------------------------------|
|  Flyers |  Internet/Web Postings |  Radio |
|  Posters |  Mass E-mail Solicitation |  Telephone |
|  Letter |  Departmental/Center Website |  Television |
|  Medical Record Review |  Departmental/Center Research Boards |  Newspaper |
|  Departmental/Center Newsletters |  Web-Based Clinical Trial Registries | |
|  YCCI Recruitment database |  Clinicaltrials.gov Registry (do not send materials to HIC) | |
|  Other (describe): please see below | | |

3. **Recruitment Procedures:**
a. Describe how potential subjects will be identified.
b. Describe how potential subjects are contacted.

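### The only allocation rule is PA-only text that cannot apply to the mixed provider cohort, and discipline is neither a stratum nor a prespecified covariate with about 10 providers per arm

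*Combined protocol and SAP*

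**What the plan says.** **Allocation.** The paragraph in Section V, item 3 that contains the rule opens as history: "Initially our main unit of randomization was the PAs within the YNHH hospitalist service". It ends with the rule itself: "a restricted randomization procedure will be used to allocate an equal number of PAs to the three conditions (10 PAs per condition"). The word restricted is not defined and no stratification factor is named.

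**Cohort.** Earlier in the same item the units are providers in general: "Specifically, we will randomize 30 Healthcare providers to one of three conditions". Section VII, item 1 (Targeted Enrollment) adds "we have expanded our target for enrollment to other Healthcare providers (i.e. nursing staff, physician, etc".) and gives the total: "Between the PAs and other healthcare providers we intend to enroll 30-40 participants". The split by discipline is not stated. The sample-size text in Section V, item 12 works with 10 per arm: "Feasibility constraints (i.e., 10 Healthcare providers per condition) limited the number of clusters".

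**Discipline.** The Research Plan says of PAs that "they spend more time interacting with their patients than physicians within the YNHH hospitalist system". Study Setting (3.C) describes usual consultation-liaison (CL) practice: "Attendings and PAs order CL services via entry into the electronic medical record". Nurses are not mentioned there.

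**Analysis.** Section V, item 12, I.2 specifies mixed models with training condition as the main predictor and a random effect for provider. Under Data reduction it plans a baseline comparison of the groups on demographics, with any unbalanced variables entered as covariates. The Clinician Survey collects provider demographics and background at baseline.

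**The concern.** The rule describes a trial that is no longer the one being run, so a reader cannot tell how nurses and physicians are assigned. Discipline could plausibly predict MI uptake on the protocol's own account: PAs and physicians differ in patient contact, and routine CL ordering, the feature that distinguishes ORDER ONE, is described only for attendings and PAs. With about ten randomised units per arm, a difference of three or four providers in discipline mix between arms would not be unusual. Part of an observed difference in uptake could then reflect who was in the arm instead of how they were trained.

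**Working it through.** **1. The plan's own figure.** The binary row of Table 2 uses 40% vs 18%, two-sided alpha 0.05 and 80% power. Per arm, n = [1.96·√(2·0.29·0.71) + 0.84·√(0.40·0.60 + 0.18·0.82)]² / 0.22² ≈ 66, so three arms need 198 (stated: 195). The design effect is 1 + (17 − 1)·0.1 = 2.6, and 195 × 2.6 = 507 (stated: 510 = 30 × 17). The table reproduces to rounding. It rests on 30 exchangeable providers and contains nothing about discipline.

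**2. Can the stated rule apply?** 3 arms × 10 PAs = 30, which is the whole cohort in Section V. With 30 providers, no place is left for a nurse or physician. With up to 40, the rule leaves up to 10 non-PAs without any allocation procedure. Either way it does not cover the mixed cohort.

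**3. Imbalance if only arm size is fixed.** Let k of 30 providers be non-PAs. The probability that the three arms receive a, b and c of them (a + b + c = k) is C(10,a)·C(10,b)·C(10,c) / C(30,k). The documents do not give k, so the range is assumed.

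| Non-PAs (k) | One given pair differs by ≥3 | DO ONE or ORDER ONE differs from SEE ONE by ≥3 |
|---|---|---|
| 6 | 17% | 27% |
| 9 | 23% | 36% |
| 12 | 26% | 41% |
| 15 | 27% | 42% |

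The last column covers the two contrasts that the hypotheses test. With k = 15, some pair among all three arms differs by at least 3 in 47% of allocations, but that figure also counts DO ONE versus ORDER ONE, which the plan treats as exploratory.

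**4. Effect on the contrast.** With equal patients per provider and the same discipline difference D in each arm, shift = (gap/10) × D. For a gap of 3 and assumed D of 10, 20 or 30 points, the shift is 3, 6 or 9 points. For scale only, Table 2's binary difference is 40 − 18 = 22 points; that is for meeting the MI performance criterion, and no effect size is stated for uptake.

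**5. Would the covariate rule catch it?** The plan gives no threshold. If a significance test were used (an assumption), 7/10 vs 4/10 non-PAs gives Fisher p = 0.37 and 7/10 vs 3/10 gives p = 0.18. Neither would be flagged at 0.05.

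**6. With stratified blocks.** Permuted blocks of three within PA and non-PA strata hold the between-arm gap in non-PAs to at most 1. If blocks of six are mixed in, an incomplete last block can leave a gap of 2. A gap of 3 cannot occur.

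**The case against.** **The rule is left-over text.** The paragraph presents the PA-only plan as the initial one, and silence on stratification does not prove its absence. This stands: the firm finding is that the procedure for the mixed cohort is not stated.

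**A literal reading would balance discipline.** A reader might infer that the plan balances PA counts and thereby leaves other disciplines unbalanced. The documents do not support that. Equal numbers of PAs in arms of equal size would also equalise the non-PAs. The percentages above apply only if arm size alone is restricted, which the plan neither states nor excludes.

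**Confounding is too strong a word.** A reader might conclude that the arms are confounded by discipline. Randomisation leaves the estimator unbiased over allocations, and the provider random effect carries between-provider variance, including any due to discipline, into the standard error. What remains is imbalance in the realised allocation and avoidable loss of precision.

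**The plan already adjusts for imbalance.** It does, and background data are collected. But the rule refers to demographics without naming discipline, has no threshold, and selects covariates after the data are seen. It is a partial remedy.

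**The assumed effects may be too large.** With a 15/15 split, a 30-point difference alone gives between-provider variance 0.30²/4 = 0.0225. At 80% uptake and ICC 0.10, the total would be 0.80 × 0.20 × 0.10 = 0.016. The top of the range therefore fits poorly with the planning values, if that ICC applies to uptake, which is not stated; 20 points (0.20²/4 = 0.010) fits. Nothing in the documents sizes a discipline effect on proficiency.

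**Nurses in ORDER ONE.** A reader might infer that nurses cannot order MI. Study Setting describes usual practice. The ORDER ONE description says that providers in that arm may order MI, and the additional assessments refer to EPIC orders placed by a provider in that arm. If ordering did differ by discipline, that would be effect modification, which a main effect would not repair.

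**Conclusion.** The concern holds in limited form. The only allocation rule cannot govern the cohort now planned, and discipline is handled neither at allocation nor by a prespecified model term. If allocation fixes arm size alone, a gap of at least 3 non-PAs in one or both primary contrasts has a probability of 27% to 42%, for an assumed 6 to 15 non-PAs among 30. The resulting shift of 3 to 9 points in uptake rests on a further assumption, a 10 to 30 point discipline difference whose top end looks high. The documents support a finding of an unspecified procedure with exposure to chance imbalance. They do not support a claim that the trial is confounded or that discipline is known to be unbalanced.

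**What to change.** 1. Reconcile Section V, item 3 with Section VII, item 1: state the allocation procedure now in force, what is restricted, the number of providers, and how disciplines are assigned, including new hires who replace leavers.
2. Stratify the allocations still open by discipline, with concealed and varied block sizes (for example 3 and 6). Blocks fixed at three would make every third assignment in a stratum deducible in an open, single-hospital trial. Define the strata explicitly, since physicians resemble PAs in CL ordering but differ from them in patient contact.
3. Prespecify discipline as a fixed effect in the primary models of Section V, item 12, in place of the imbalance-triggered rule for this variable. This also covers providers already randomised.

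The cost is a revised allocation list and one between-provider degree of freedom for a two-level factor (two for three levels). Arm totals may depart slightly from 10 if the last blocks are incomplete. The targets of 30 providers and 1,200 patients do not change.

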Healthcare providers in this condition will participate in a 1-day skill-building workshop. [name], a member of the Motivational Interviewing Network of Trainers (MINT) and a highly experienced MI workshop trainer, will conduct the workshop per MINT recommendations, giving the Healthcare providers an opportunity to "see" the MI intervention and learn how to conduct it through expert and

video demonstrations and experiential activities. He also will teach the Healthcare providers how to screen patients for risky substance use with NIAAA Guidelines, the CAGE Questionnaire and Heaviness of Smoking Index¹¹⁴ (described below). A 2-hr “booster” session will be provided to Healthcare providers once they have reached their halfway point of the trial phase (20 eligible patients), consistent with the common practice of requiring annual refresher training for critical procedures used by staff in hospitals.

2. Workshop plus live supervision (Do One)

Healthcare providers will participate in a 1-day skill-building workshop conducted by [name], including halfway point booster sessions, as outlined above. Following the workshop, the Healthcare providers will each “do one” MI intervention under the live supervision of a Psychiatrist from CL. [name] will have taught the CL psychiatrists to conduct MI and will have trained them in the supervisory practices developed in our prior MI training work (See Appendix B).^{21,89,90} Healthcare providers can request additional live supervision at any point during the trial, consistent with the apprenticeship model.¹³⁻¹⁶ Additionally, once the Healthcare provider in this condition reaches their halfway point of the trial phase (20 eligible patients), they will be offered another bedside supervision as a refresher of their MI skills.

3. Workshop plus consultation-liaison service (Order One)

Healthcare providers will participate in a 1-day skill-building workshop and annual booster sessions conducted by [name]. The Healthcare providers in this condition will be instructed that they may either administer MI or they may “order” a MI interview to be delivered by a Psychiatrist from CL with specialty MI training. This is the only group that may “order” a MI interview.

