Before Healthcare providers can “order” MI from CL, [name] will train and supervise the CL Psychiatrists in MI, who will provide adequate coverage for administration of MI during the data collection period of the project. Training will follow a clinical trials training approach used in efficacy and effectiveness trials:^{115,116} 1) a 2-day skill-building workshop; 2) three post-workshop supervised practice cases based on review of audio recorded sessions using the NIDA-SAMHSA MI supervision blending product, MIA: STEP,^{86,94}; and 3) follow-up monthly individual supervision to maintain and monitor the CL experts’ MI practice.

4. Rationale for implementation strategy choice and study design

Continuing medical education workshop/seminar training plus booster sessions is the usual approach for teaching medical professionals new or unfamiliar clinical practices^{70,71} and will serve as our control condition. By holding this training constant across conditions, we can isolate the effects of live-supervision in DO ONE and ability to order MI from CL in ORDER ONE that exceed those which occur in primary care training-as-usual efforts. We considered a two cell design that would compare DO ONE and ORDER ONE. However, to our knowledge neither DO ONE or ORDER ONE have been tested in primary care settings. Given this, we felt that a true “control condition” by which to compare uptake, MI proficiency, and cost effectiveness is required.

5. Rationale for sample choice:

We are recruiting a heterogeneous sample of substance using patients to test the implementation strategies in clinical circumstances typically seen by Healthcare providers on general medical inpatient units. Finally, most Healthcare providers and all MI integrity raters are mono-lingual English speakers. We therefore do not have the capacity to include Spanish-only speaking patients in the study.

G. Procedures for monitoring Healthcare provider-patient assignments and audio recording MI interventions

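### Booster training is triggered at 20 patients in SEE ONE and DO ONE but yearly in ORDER ONE, although the design rationale says this training does not differ between arms

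*Combined protocol and SAP*

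**What the plan says.** The three conditions are described in Section V, item 3 (Research Plan).

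- **Workshop (See One):** a 1-day workshop, then one 2-hour booster for providers "once they have reached their halfway point of the trial phase (20 eligible patients"). The sentence goes on to call this "consistent with the common practice of requiring annual refresher training for critical procedures used by staff in hospitals".
- **Workshop plus live supervision (Do One):** the same workshop, "including halfway point booster sessions, as outlined above".
- **Workshop plus consultation-liaison service (Order One):** a "1-day skill-building workshop and annual booster sessions conducted by" the trainer. No patient count, number of sessions or length is given, and there is no reference back to the SEE ONE description.

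The next subsection, Rationale for implementation strategy choice and study design, defines the control training: "Continuing medical education workshop/seminar training plus booster sessions is the usual approach". It then states the inferential purpose: "By holding this training constant across conditions, we can isolate the effects of live-supervision in DO ONE and ability to order MI from CL". The training said to be constant therefore includes the boosters.

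**The concern.** One rule runs on caseload and the other on the calendar. Follow-up of a provider ends at 40 enrolled patients, not at a date, so the two rules are not interchangeable.

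The rationale makes constant training the reason why a difference between ORDER ONE and SEE ONE can be credited to the ordering option. If the booster schedule also differs, that contrast has two components. It is tested on uptake (H1b) and on proficiency (H2b), both under the primary aims.

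The exposure differs by hypothesis:

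- **H2b.** The Background says that workshop gains in MI integrity can fade within 2-3 months without further training, so the protocol itself treats follow-up training as relevant to proficiency. In ORDER ONE, "healthcare providers may elect to conduct MI themselves or order it to be conducted by Psychiatrists from the CL service". Only the sessions that providers conduct themselves are directly exposed, because the CL psychiatrists have their own training and monthly supervision.
- **H1b.** The Background statement concerns integrity, not uptake. An effect on uptake is possible but not documented.
- **H3.** The cost form records labour hours as delivered, so booster cost would be captured. It would, however, reflect a schedule that the other arms do not have.
- **H1a and H2a.** Unaffected, because DO ONE and SEE ONE share the booster rule. The extra bedside supervision offered to DO ONE at the halfway point is part of that arm's strategy and is not a further inconsistency.

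**Working it through.** No planned figure depends on the booster, so there is nothing to reproduce. The check sets the texts side by side and then asks how far the two rules diverge.

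**Text comparison**

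| | SEE ONE | DO ONE | ORDER ONE | Design rationale |
|---|---|---|---|---|
| Workshop | 1 day | 1 day | 1 day | constant |
| Booster trigger | 20 patients | 20 patients (by reference) | yearly | constant |
| Booster length | 2 hours | by reference | not given | constant |

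Only the booster entry differs between arms. It conflicts with the last column.

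**Inputs.** Caseload: 40 patients per provider. Halfway trigger: 20 patients. Let T be the months from a provider's workshop to patient 40. T is not stated and is an assumption here. Its upper limit is taken from the 4-year data collection phase ("nets 40 PAs during the 4-year data collection phase of the project"), so T is at most 48. Two further assumptions: accrual is even, and the yearly clock starts at each provider's workshop.

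**Formulas**

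- Halfway rule: 1 booster at patient 20, with 20 of 40 patients after it, for any T.
- Yearly rule: boosters at months 12, 24, ... before T. The count is ceil(T/12) − 1. The k-th booster falls at patient 40 × 12k/T. Patients after the first booster are 40 × (1 − 12/T) if T > 12, otherwise 0.

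**Results for ORDER ONE under the yearly rule**

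| T (months) | Boosters before patient 40 | Caseload position | Patients after first booster |
|---|---|---|---|
| up to 12 | 0 | none | 0 |
| 18 | 1 | 40 × 12/18 = 26.7 | 13.3 |
| 24 | 1 | 40 × 12/24 = 20 | 20 |
| 36 | 2 | 13.3 and 26.7 | 26.7 |
| 48 | 3 | 10, 20 and 30 | 30 |

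The comparator in SEE ONE is always 1 booster, at patient 20, with 20 patients after it. The yearly rule gives exactly one booster for T above 12 and up to 24 months. Its position, 480/T, equals 20 only at T = 24.

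**Alternative reading.** If yearly means fixed dates for the whole arm, the count is floor(T/12) or ceil(T/12), depending on when the provider starts. A provider taking 8 months gets 0 or 1, and one taking 18 months gets 1 or 2.

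**How plausible is the range of T?** The document gives figures that point in both directions. The hospitalist service had about 9,900 discharges in 2010 and has 33 PAs. If shared evenly, that is 9,900/33 = 300 per PA per year, so enrolling 40/300 = 13% of them would fill a caseload in 12 months. Conversely, if all 30 providers were active throughout and the 1,200 patients accrued evenly over 48 months, each would gain 1,200/(30 × 48) = 0.83 patients a month, and 40/0.83 = 48 months. Neither enrolment share nor staggering of providers is stated, so the document does not settle T.

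**The case against.** The strongest reply is that this is a drafting leftover. The SEE ONE sentence itself compares the halfway booster with yearly refresher training, DO ONE carries the halfway wording, and ORDER ONE may simply not have been updated. The rationale states the intention plainly. This explanation is plausible, and the documents do not show that the arms were trained differently. It does not remove the discrepancy: in SEE ONE the yearly phrase is an analogy and the operative rule is 20 patients, whereas in ORDER ONE yearly is the operative rule. Workshops are run separately by condition, so staff who follow the ORDER ONE paragraph would schedule by calendar.

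A second reply is that H1b and H2b compare conditions as assigned, and randomisation keeps those comparisons valid whatever the booster schedule. That is right. What is lost is the attribution of a difference to ordering, which is exactly what the rationale claims.

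A third is that it is no defect for the planned mixed model, with condition as main predictor, to lack a term for boosters, because a rule set by arm is aliased with arm. That also stands. The problem has to be settled in the protocol, not in the model.

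Finally, the table counts sessions under an assumed T and does not measure bias. This is true, and it limits the weight of the point but not its correctness.

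**Conclusion.** The concern holds. The ORDER ONE booster wording and the claim of constant training cannot both stand, and no other section reconciles them.

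If the text is followed, ORDER ONE providers receive between 0 and 3 boosters over their caseload, against 1 in the other arms. Between 0 and 30 of their 40 patients come after a first booster, against 20. The schedules match in number and timing only for a provider who takes 24 months. These figures rest on even accrual, a clock starting at the workshop and T of at most 48 months. Whether ORDER ONE gets less or more booster training depends on accrual speed.

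The size and direction of any effect on uptake or proficiency cannot be derived from the documents. Confidence is high in the mismatch and in what the contrast would then contain. There is no basis for saying that results would be materially changed. The point should be corrected, but it does not undermine the randomised comparison itself.

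**What to change.** Reconcile the three condition descriptions with the design rationale, in one of two ways:

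1. State a single booster trigger, number and length that applies to all three arms, whichever the team adopts.
2. If the difference is intended, remove the statement that training is constant, describe the booster schedule (with number and length) as part of the ORDER ONE strategy, and say that H1b and H2b estimate the effect of the whole package.

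In either case, record the date of each booster per provider, and report by arm the number received and where they fell in the caseload. Do not adjust the outcome models for booster exposure: it arises after randomisation, and under the stated rule it is fixed at one in SEE ONE.

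The cost is a wording change in two adjacent subsections, plus a date entry per booster kept alongside the activity time form already planned under Cost estimates, and a short descriptive table. Sample size and analysis models do not change.
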